5.3 Study discontinuations

The following information will be summarized for the randomized patients by treatment and overall:

- Study completers,
- Total length of study from randomization,
- Subjects who discontinued the study prematurely (and reasons),
- Subject who completed the IMP
- Subjects who discontinued the IMP (and reasons),
- Subjects who discontinued the IMP but completed the study,
- Subjects who discontinued the IMP and discontinued the study prematurely,
- Broken randomization code (and reasons).

If more than 30% of randomized subjects overall discontinue the study prematurely, the distribution of the time from randomization to discontinuation will be summarized using time-to-event method.

5.4 Demographics and baseline characteristics

The baseline demographic characteristics will be summarized by treatment and overall, by means of descriptive statistics on the RND set. In the case the RND set is not the same as FAS set, the summary of baseline characteristics will be replicated on FAS set. No statistical testing will be carried out for demographic or other baseline characteristics.

The following demographic information will be reported:

- Geographic region of the site (Europe, US), country within region, and sites within country.
- Age (years).
- Age class (<40 yrs, 40 – 64 yrs, ≥ 65 yrs).
- Sex (Male, Female).
- If female,
 - Potential childbearing (Childbearing potential, Postmenopausal with no menstrual bleeding for at least one year prior to study start, surgically sterilized).
 - Contraception method (s).
 - Was the pregnancy test performed? (Yes, No)
 - If yes,
 - Result of urine dipstick (Negative, Positive)

Standard/Forms/Template				
Title		Statistical Analysis Plan Template		
Code		Version	Effective Date	Page
PPD		01	29 Aug 2022	36 of 78

- If positive,
 - confirmed by performing the serum pregnancy test? (Yes, No)
 - If yes,
 - Result of serum pregnancy test
- Race/Ethnicity (White, Black or African American, Asian, Hispanic or Latino, Other);
- Height (cm),
- Weight (Kg)
- BMI (kg/m²)
- BMI (BMI≤25kg/m², 25kg/m²<BMI≤30kg/m², BMI>30kg/m²).

The following information on use of substances will be reported:

- Has the patient ever consumed alcohol? (Never, Former, Current)
- If former or current
 - Amount of alcohol consumed daily (< 1 Liter of wine (or equivalent), ≥ 1 Liter of wine (or equivalent))
 - Approximate duration of alcohol consumption (years)
- Has the patient ever used tobacco? (Never, Former or Current);
- If former or current
 - Amount of cigarettes consumed daily (<10 cigarettes (or equivalent), ≥10 cigarettes (or equivalent))
 - Approximate duration of tobacco consumption (years)

The following information on influenza virology will be reported:

- Has the patient been recently tested for influenza? (Yes, No)
- If yes,
 - Influenza test result (Positive or Negative);

The following specific information on COVID-19 will be reported:

- Did the patient receive vaccination for COVID-19? (Yes, No).
- If yes:
 - Received vaccine(s)
 - Last vaccine received
 - Time from Date of last COVID-19 vaccination to randomization
 - Total number of doses received
- Time from Date of diagnosis of moderate to severe ARDS as defined in inclusion criterion 3 to randomization
- Time from hospital/ED admission to randomization

5.5 Medical and surgical history

Standard/Forms/Template				
Title		Statistical Analysis Plan Template		
Code		Version	Effective Date	Page
PPD		01	29 Aug 2022	37 of 78

A disease is classified as:

- “Medical/Surgical history” if it is not ongoing at screening visit.
- “Concomitant disease” if it is ongoing at screening visit.

Medical/Surgical history and/or concomitant diseases will be coded using Medical Dictionary for regulatory activities (MedDRA, Version 25.0 or later) dictionary and reported in separate tabulations. Frequency distributions and percentages will be summarized by treatment, by System Organ Class (SOC) and Preferred Term (PT), sorted in decreasing order of total frequency on the RND set. In the case the RND set is not the same as FAS set, the summary of baseline characteristics will be replicated on FAS set. Counts will be given for both SOC and PT by subject. Subjects experiencing more than one previous/concomitant disease event will be counted only once within each SOC and PT.

5.6 Prior and concomitant medications

Based on the start/end medication date(s) reported in the eCRF (see Table 5 for derivation rules), a medication will be defined as:

- “Prior medication” if stopped in the 7 days before the screening or, however, prior to administration of the first dose of study treatment.
- “Other Prior medication” if stopped prior to 7 days before the screening.
- “Concomitant medication” if taken on or after the administration of the first dose of study treatment. In particular, all medications which start prior to, on or after the first administration of study treatment and start no later than date of study completion or discontinuation and end on or after the first administration of study treatment or are ongoing at the study completion or discontinuation are considered.

In case of missing information not directly allowing allocation to either of the three above categories of medications, the medication will be considered as concomitant.

Prior and/or concomitant medications will be coded using World Health Organization Drug Dictionary (Version March 2022, or later) and reported in separate tabulations.

Frequency distributions and percentages will be summarized by treatment, by Anatomical Main Group (1st level of the Anatomical Therapeutic Chemical (ATC) classification), Chemical Subgroup (4th level of the ATC classification) and Preferred Name, sorted in decreasing order of total frequency on the RND set and SAF set. In the case the RND set is not the same as FAS set, the summary of baseline characteristics will be replicated on FAS set. Subjects taking more than one medication classified in the same category will be counted only once. Other Prior medication category will only be listed.

Standard/Forms/Template				
Title		Statistical Analysis Plan Template		
Code		Version	Effective Date	Page
PPD		01	29 Aug 2022	38 of 78

5.7 Other baseline characteristics

Other baseline characteristics will be summarized by treatment and overall, by means of descriptive statistics on the RND population. In the case the RND set is not the same as FAS set, the summary of baseline characteristics will be replicated on FAS set.

5.7.1 Lung function

Baseline lung function parameters:

- SpO₂ (%),
- SaO₂ (%),
- PaO₂ (mmHg),
- PaCO₂ (mmHg),
- FiO₂ (0.21 to 1),
- PaO₂/FiO₂ ratio (mmHg) ,
- SpO₂/FiO₂ (derived)

will be descriptively summarized by treatment and overall as a continuous variable.

Investigator's interpretation (Normal, Abnormal NCS, Abnormal CS, No Result) for SpO₂ (%), SaO₂ (%), PaO₂ (mmHg) and PaCO₂ (mmHg) will be reported as well. Information on the lung function assessment (performed/not performed) will be reported, with reasons in case of not execution.

5.7.2 Chest imaging

Information on chest imaging baseline assessment will be summarized by treatment and overall, by means of descriptive statistics. Information on the assessment (performed/not performed) will be reported, with reasons in case of not execution. The following information will be reported:

- Method (X-rays, CT scan)
- Confirmation of lung involvement and inflammation (Yes, No)
- Clinical evaluation(s)
- Number of quadrants with alveolar infiltrates

5.7.3 SOFA Score

Information on SOFA score baseline assessment will be summarized by treatment and overall, by means of descriptive statistics. Information on the assessment (performed/not performed) will be reported, with reasons in case of not execution. Up to CRF V6.0, sites entered in eCRF the single items and the SOFA score was automatically calculated. Starting from CRF V7.0 sites have either 1) the possibility to complete the single items (if they are all available) and get the SOFA Score automatically calculated

Standard/Forms/Template				
Title		Statistical Analysis Plan Template		
Code		Version	Effective Date	Page
PPD		01	29 Aug 2022	39 of 78

OR

2) they can enter the total SOFA score manually, without completing the single items.

Summaries will not differentiate between these two methods of collecting the total SOFA score (i.e. will report the total score regardless if it is manually entered or automatically calculated from single items).

If both scores (manually and automatically calculated) are present, the value automatically calculated will be used in the analysis.

5.7.4 Child Pugh Score and Class

Baseline Child Pugh Score, when applicable, will be descriptively summarized by treatment and overall as categorical variable with the classes A: 5-6, B: 7-9, C: 10–15. Information on the Child Pugh Score assessment (performed/not applicable/ not performed) will be reported, with reason in case of not execution.

5.7.5 Mechanical ventilation parameters

Information on Mechanical ventilation assessment will be summarized by treatment and overall, by means of descriptive statistics. Information on the assessment (performed/not performed) will be reported, with reasons in case of not execution. The following baseline information will be reported:

- Ventilator mode,
- Tidal volume (mL),
- Ventilator Rate,
- PEEP (cmH₂O),
- Mean airway pressure (cmH₂O),
- Plateau airway pressure (cmH₂O)
- Dynamic Compliance (mL/cmH₂O)

With regards to ventilator mode, the classes will be grouped together as follows. Any further data collected not falling in the classification below will be discussed with the clinical team and classified accordingly.

Standard/Forms/Template				
Title		Statistical Analysis Plan Template		
Code		Version	Effective Date	Page
PPD		01	29 Aug 2022	40 of 78

Ventilator mode	
Classes (UPPERCASE)	Grouped Classes
AC AC/VC ASSIST CONTROL FULL MECHANICAL VENT SUPPORT A/C ASSIST CONTROL A/C A/C PC AC VC AC, Volume Control AC/Pressure Control (S)CMV CMV VOLUME AC/S VOLUME A/CS CMV ASSIST CONTROL VOLUME AC/S CMV	CMV, volume control
BIBAP BIPAP PC-BIPAP	BIPAP
APRV APV APV CMV AIRWAY PRESSURE RELEASE VALVE APRV BIVENT APRV BIVENT_AP RV BIVENT AP RV	APRV
SIMV PC	SIMV PC
PRESSURE SUPPORT PS CPAP-PS	Pressure support

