2. SCHEDULE OF EVALUATION

The grid below summarizes the study schedule of the trial. For all measurements, the actual date and time of assessment, including date of sampling, will be recorded in the Source Document and/or eCRFs. Timeframe for each assessment is also shown in the grid below.

Days (windows)	Screening (day-1 or 1)	Randomization and baseline assessments ¹	Day 1	Day 2 (±8h)	Day 3 (±8h)	Day7 (±1)	Day 14 (±2)	End of Treatment ²	Extubation to Hospital Discharge (every 48h±8h)	Day 28 (±2) and Hospital Discharge ¹⁹	Day 60
ELIGIBILITY											
Informed consent signed	X										
Demo-graphics, Medical History, Disease-Specific Information, allergies	X										
Pregnancy test ²	X										
STUDY INTERVENTION											
Randomization		X									
IMP administration ³			Daily through day 14 with the option to extend to day 21								
STUDY PROCEDURES											
Vital signs (RR, HR, MAP)			Daily through extubation				X				
PaO ₂ (or SaO ₂), FIO ₂	X		Daily through extubation				X	X			
PaCO ₂			Daily through extubation								
Mechanical ventilation parameters ⁴			Daily through extubation								
SOFA score			Daily through extubation								
Neuromuscular blocking agents, inhaled vasodilators ⁵			Daily through extubation								
Prone positioning ⁶			Daily through extubation								
Vasoactive medications ⁷			Daily through extubation								
ECMO ⁸			Daily through extubation								
CPAP attempts ⁹			Daily through extubation								
Chest imaging ¹⁰	X	X	X	X	X	X					
Biomarkers ¹¹		X		X	X	X					
Reintubation ¹²									X		
Other clinical events ¹³									X		
Follow up ¹⁴										X	
SAFETY TESTS											
Adverse events	↔										
Concomitant medications	↔										
Safety hematology and	X				X	X	X	X		X	

Days (windows)	Screening (day-1 or 1)	Randomization and baseline assessments ¹	Day 1	Day 2 (-8h)	Day 3 (-8h)	Day 7 (±1)	Day 14 (±2)	End of Treatment ²¹	Extubation to Hospital Discharge (every 48h±8h)	Day 28 (±2) and Hospital Discharge ¹⁹	Day 60
biochemistry ¹⁵											
eGFR ¹⁶	X			X	X	X	X			X	
Hepatic function ¹⁷	X			X	X	X	X				
ECG	X			X	X	X	X				X ²¹
CCI											

1. Baseline and initiation of IMP (day1) may coincide
2. In females of childbearing potential, only date will be required
3. Study product will be administered every 8 hours (q8h) for 14 days, and optionally up to 21 days
4. Mode of ventilation, TV, mean airway pressure, plateau airway pressure, PEEP
5. Use or not of neuromuscular blocking medications and/or inhaled vasodilators

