7. STUDY ENDPOINTS

7.1. EFFICACY ENDPOINTS

Primary endpoint:

- Change in oxygenation index (**OI**) from baseline to day 7 of treatment. The OI is defined as: % mean airway pressure x $\text{FIO}_2/\text{PaO}_2$
- Ventilator free days (**VFD**) at day 28 (see 14.4.11)

[figure not shown]
Secondary endpoints:

- Change in OI from baseline to day 4
- Acute lung injury score [composite of $\text{PaO}_2/\text{FIO}_2$ ratio, PEEP, lung compliance (plateau airway pressure minus PEEP/TV) and extent of pulmonary infiltrates] at 2, 3, 7, 14 days (if still intubated)
- SOFA scores at 2, 3, 7, 14 days (if still intubated)
- Ventilatory ratio (product of minute ventilation and PaCO_2) at 2, 3, 7, 14 days (if still intubated)
- Incidence of ECMO at day 14
- Use of vasoactive medications at day 14
- CXR assessment of pulmonary edema by “radiographic assessment of lung edema” (**RALE**) score at 2, 3, 7, 14 days
- Percentage of patients achieving pressure support ventilation equal to 5 cm H₂O with PEEP equal to 5 cm H₂O for 2 hours (measure of weaning) by day 28 and hospital discharge
- ICU-free days by day 28 and hospital discharge
- Hospital-free days by day 28 and hospital discharge
- Incidence of tracheostomies by day 28 and hospital discharge
- Incidence of LTAC facility by day 28 and hospital discharge
- All-cause mortality by day 28
- Hospital discharge by day 28
- All-cause mortality by day 60
- Change from baseline to day 3, 7 and 14 in plasma levels of IL-6, IL-8, PAI-1, Plasma TNFr-1, ICAM-1 RAGE

Footnote: day 1 is the day when the IMP is first administered. Hour 1 of day 1 starts when the first dose of the IMP is administered. Subsequent days are measured in 24-hour intervals from hour 1. Therefore, day 2(± 8 h) signifies 24 hours ± 8 hours from hour 1.

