14.4.5. Acute lung Injury Score

Component	0	1	2	3	4
Chest X-ray (Alveolar infiltrates)	No	1 quadrant	2 quadrants	3 quadrants	4 quadrants
Hypoxaemia ($\text{PaO}_2/\text{FiO}_2$, mmHg)	≥ 300	225–299	175–224	100–174	≤ 100
PEEP (PEEP-setting, cmH_2O)	≤ 5	6–8	9–11	12–14	≥ 15
Compliance (Static, $\text{mL}/\text{cmH}_2\text{O}$)	≥ 80	60–79	40–59	30–39	≤ 29

From: Murray JF et al. An expanded definition of the adult respiratory distress syndrome. Am Rev Respir Dis 1988;138:720-3

The final score is obtained by dividing the collective score by the number of components that were used.

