Compliance	40-59.99 ml/cmH ₂ O	2																																																																																		
Compliance	30-39.99 ml/cmH ₂ O	3																																																																																		
Compliance	≤ 29.99 ml/cmH ₂ O	4																																																																																		
	Score																																																																																			
No lung injury	0																																																																																			
Mild-to-moderate lung injury	0.1-2.5																																																																																			
Severe lung injury (ARDS)	>2.5																																																																																			

Standard/Forms/Template				
Title		Statistical Analysis Plan Template		
Code		Version	Effective Date	Page
PPD		01	29 Aug 2022	72 of 78

Parameter	Calculation

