	
PaO₂/FiO₂ (mmHg) is collected under "Lung Function" at "Screening day -1 or 1", "randomization and baseline assessments", during the "daily assessment through extubation", during "assessments from extubation to hospital discharge (every 48h+/-8h)", at day 28 and at hospital discharge.
 
PEEP (cmH₂O) and Compliance (ml/cmH₂O) is collected under "Mechanical Ventilation Parameters" at "randomization and baseline assessments" and during the daily assessment through extubation. Mechanical Ventilation Parameters are collected at a specific date and time
 
Rules to match assessments for Acute Lung Injury score:
 
 1. keep date of Chest Imaging assessment from the i-th visit (namely, day 2,3,7,14) 2. link date of LF (Lung Function) and MV (Mechanical Ventilation) assessments with the date of CI (Chest Imaging), i.e., the assessments should be at the same date. 3. If no link is feasible Acute Lung Injury Score at that Visit will be missing. 
If chest imaging date is missing, please use study day based on date/time as follows:
 
Select the value of Lung Function assessment based on the study day rules considering date and time. Select the value Mechanical Ventilation assessment based on the study day rules considering date and time. If there is one measurement of LF and one measurement of MV falling in that specific study day (as defined by the rules considering date/time), select these values to compute the Acute Lung Injury score at that day. Do the same for each applicable post baseline day. (Example for day 7. Both LF and MV assessments should be collected in the window [First IMP Intake+132h, First IMP Intake+155h and 59min]). In case of more assessments at the same day, keep the assessment closer to the midpoint of the time interval. For instance: 2 assessments at day 7 [First IMP Intake Date/Time +132h, First IMP Intake Date/Time +155h and 59 min], the one closer to 144 hours from 1st IMP will be taken. If multiple records exist at the same distance from the midpoint of the time interval, select the first record collected in the eCRF.

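### The SAP names no valid source for the static compliance item of the acute lung injury score: the only compliance field it lists is dynamic, and its written expression is inverted

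*SAP*

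**What the plan says.** - Protocol 14.4.5 gives the scoring table. The compliance row is headed "Compliance (Static", in mL/cmH2O, with 0 points at 80 or more, 1 at 60–79, 2 at 40–59, 3 at 30–39 and 4 at 29 or less.
- Protocol 7.1 lists the score as a secondary endpoint and describes the item as "lung compliance (plateau airway pressure minus PEEP/TV". SAP 3.5.2 and 11.1.1 repeat that description.
- SAP 11.1.1 keeps the protocol's compliance cut-offs (the worst category is "≤ 29.99 ml/cmH ₂ O") but drops the word static. On the data source it says "PEEP (cmH₂O) and Compliance (ml/cmH₂O) is collected under" the Mechanical Ventilation Parameters form. It gives no rule for computing the item from tidal volume, plateau pressure and PEEP.
- SAP 5.7.5, whose title matches that form, lists the parameters to be summarised at baseline. The only compliance among them is "Dynamic Compliance".
- The protocol schedule (Section 2, footnote 4) lists the ventilation parameters as "Mode of ventilation, TV, mean airway pressure, plateau airway pressure, PEEP". It lists neither a compliance field nor peak pressure.
- The score is the mean of the available items: "The final score is obtained by dividing the collective score by the number of components that were used". SAP 11.1.1 requires at least three of the four and classes a score above 2.5 as severe.

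**The concern.** A programmer following SAP 11.1.1 would look for a collected compliance field, and the only one named in the SAP is dynamic. Static and dynamic compliance are different quantities. In the usual definitions, static compliance divides tidal volume by plateau pressure minus PEEP, and dynamic compliance divides it by peak pressure minus PEEP. The dynamic value therefore also reflects airway resistance and flow. Static cut-offs applied to it would place some patients in a worse category than the protocol's table intends.

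The endpoint text does not settle the matter, because its expression is pressure over volume, the reciprocal of compliance. At stake are the level of the score at Days 2, 3, 7 and 14, its change from baseline, and the severity classes and shift table in SAP 7.2.1.2.

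**Working it through.** The plan states no figure for this point, so there is none to reproduce. The cut-offs, the averaging rule and the 2.5 line come from Protocol 14.4.5 and SAP 11.1.1. Everything else below is assumed: the peak-pressure definition of dynamic compliance, tidal volume (TV), the pressures, and the peak-plateau gap R.

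**1. Direction.** Static = TV/(plateau − PEEP). Dynamic = TV/(plateau + R − PEEP). Since R ≥ 0, dynamic ≤ static, so the points can only stay the same or rise.

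**2. Single cases** (TV 420 mL, PEEP 10 cmH2O):

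| Plateau | Static | R | Dynamic |
|---|---|---|---|
| 24 | 420/14 = 30.0, 3 points | 4 | 420/18 = 23.3, 4 points |
| 24 | 30.0, 3 points | 8 | 420/22 = 19.1, 4 points |
| 20 | 420/10 = 42.0, 2 points | 4 | 420/14 = 30.0, 3 points |
| 20 | 42.0, 2 points | 8 | 420/18 = 23.3, 4 points |
| 28 | 420/18 = 23.3, 4 points | 8 | 420/26 = 16.2, 4 points |

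**3. Effect on score and class.** One category is worth 1/4 = 0.25 with four items and 1/3 = 0.33 with three. With the other items at 3, 3 and 2, two compliance points give (8 + 2)/4 = 2.50 (mild-to-moderate) and three give (8 + 3)/4 = 2.75 (severe).

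**4. Range over R.** Static compliance is taken as normal with mean/SD 30/10, 35/12 or 45/15 mL/cmH2O, limited to 10–120, with TV 420 mL. The ranges run across these three distributions:

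| R (cmH2O) | Share moving to a worse category | Mean rise, four-item score |
|---|---|---|
| 0 | 0% | 0 |
| 2 | 33–50% | 0.08–0.13 |
| 5 | 50–84% | 0.15–0.29 |
| 10 | 50–84% | 0.16–0.41 |

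Between 16% and 50% of patients already score 4 on static compliance and cannot move. No patient moved to a better category.

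**5. Ceiling.** Take TV 420 mL and R = 4. Static compliance improving from 25 to 35 goes from 4 points to 3. The driving pressures are 420/25 = 16.8 and 420/35 = 12, so dynamic compliance is 420/20.8 = 20.2 and then 420/16 = 26.3. Both score 4, and the improvement disappears.

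**6. The written expression.** Read as (plateau − PEEP)/TV, the three plateau values above give 10/420 = 0.024, 14/420 = 0.033 and 18/420 = 0.043. Each is far below 29.99, so every patient would score 4. The units of the cut-offs show that this is not intended, but the expression cannot serve as the derivation rule.

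**The case against.** The strongest reply is that no sentence puts the dynamic value into the score. SAP 11.1.1 says only compliance and, in the same entry, repeats the plateau-based description, which points to static. SAP 5.7.5 is a list of baseline summaries, not a derivation rule, and it does not claim to list every field on the form. The eCRF is not among the documents, so dynamic could be a mislabel, or the form could hold two compliance fields. The SAP revision history and two bullets of SAP 4.11 are redacted and might address the item. All of this stands. A reader might infer that the score will be computed from dynamic compliance and that severity is overstated; the documents do not establish either.

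The effect on the trial is also limited. Secondary endpoints are descriptive, and SAP 7.2.1 tests continuous ones only as change from baseline. The same rule would apply in both arms and at baseline, so part of any shift may cancel. Cancellation need not be complete, because the ceiling works against improvement and the peak-plateau gap can vary between visits and ventilator modes.

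The inverted ratio taken alone is editorial. What the reply does not remove is the gap itself: the SAP gives neither a usable formula nor a named static field for this item.

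**Conclusion.** The point holds as a conflict between the protocol's static item and the SAP's data source, and it should be resolved. It does not show that any score will be wrong.

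If the dynamic field is used, the direction is certain under the usual definition: the same category or a worse one. The size depends on the peak-plateau gap, which the documents do not give. It is zero at no gap, about 0.08–0.13 points on the four-item score at 2 cmH2O, and 0.15–0.29 at 5 cmH2O, under the assumed distributions. Only patients who cross a cut-off are affected, and those at or below 29.99 do not shift. The severity classes and the shift table are the most exposed. Oxygenation index and ventilator-free days do not use compliance and are unaffected.

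**What to change.** In SAP 11.1.1:

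- Derive the compliance item at baseline and at Days 2, 3, 7 and 14 as tidal volume/(plateau pressure − PEEP) from the collected values.
- When plateau pressure is unavailable, treat the item as missing under the existing three-of-four rule.
- Restore the word static in the scoring table.
- Write the expression as volume over pressure, here and in the endpoint text of Protocol 7.1 and SAP 3.5.2.
- Check the eCRF label of the field summarised in SAP 5.7.5. Use the collected field in the score only if it is confirmed to be static compliance.

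No new data are needed, since Protocol 6.1.2 and 6.1.3 collect all three inputs at baseline and daily until extubation. The cost is a revised derivation entry and reprogramming of one item. Because the SAP is already at Final 2.0, this means a further version or a documented deviation in the study report, preferably settled before unblinding. Where plateau pressure is missing, the score will rest on three items.
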